#### Autonomy:

The evolution of the EBS (autonomous eating), GIR and Blandford scale (physical or psychological autonomy) scores between inclusion and 6 months will be compared between the 2 groups by a Wilcoxon Mann-Whitney test.

#### Resident satisfaction/enjoyment of food:

The evolution of the satisfaction VAS between inclusion and 6 months will be compared between the 2 groups by a Wilcoxon Mann-Whitney test.

### Hospitality/care load of seniors's residents professionals:

Changes in meal duration and the number of professional interventions between inclusion and 6 months will be compared between the 2 groups by a Wilcoxon Mann-Whitney test.

### 6.2.2 Statistical justification of the number of inclusions

To our knowledge, no clinical study has been carried out on the impact of "finger-food" in seniors's residents. Therefore, we have no data available that would allow us to make working hypotheses on its impact on the nutritional status of patients.

The purpose of this pilot study is therefore to collect preliminary data on the nutritional evolution of these patients.

No statistical calculations were performed. All residents of the 6 participating seniors's residents who met the inclusion criteria were included in the study.

### 6.2.3 Expected level of statistical significance

The significance level is set at 5%.

### 6.2.4 Statistical criteria for discontinuation of study

NA

### 6.2.5 Consideration method for missing, unused or invalid data

The main criterion being the comparison of the evolution of the quantity of ingesta between the inclusion and the 6 months of follow-up, a missing value of these data will entail an imputation of this one by the worst value then, by the average of its group.

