### 2.1.3 Primary endpoint

Quantitative measurement of ingesta (caloric and protein intake), monthly between M-1 (before implementation of the "finger-food") and M6.

The assessment of nutritional intakes will be carried out on 3 consecutive days, by a dietician, for lunch and dinner, at a point in time between M-1 and M0 (i.e. before the implementation of the "eat-in" system), and then monthly.

This dietary assessment will be done by means of photos BEFORE/ AFTER the consumption of the meal, by the housekeepers. The photos will target the actual consumption of the meal compared to the proposed service. This tool is preferred to the food monitoring form, usually used in the seniors's residents, but which does not allow for a detailed analysis of the food consumed and the quantities per dish actually ingested by the residents.

Also, the environment of the meal will be photographed in order not to wrongly consider the possible food losses, notably food on the ground, as food contributions. The residents' faces will not be photographed.

Information on the taking of these photographs will be provided to the appropriate people in order to have an image quality that is conducive to analysis and to respect a certain homogeneity of distance in the taking of photographs and in the analysis that will result from them.

The same dietician will ensure the analysis of the photos and intakes to avoid bias.

The photos will be analyzed using a quantitative and qualitative approach:

Meal consumption: A global evaluation of the meal will be done according to whether the resident ate all of his meal, /4, half, /4 of his meal or nothing at all, while taking

into account the environment.

- Type of dish consumed (starter / main course: meat-fish-egg, vegetable-starch / dairy product / dessert).
- The caloric (in kilocalories) and protein (in grams) intakes of the meal trays will be calculated before distribution to the residents.
- The same calculations will be made after the meal has been consumed, taking into account the environment and what the resident has actually eaten. They will be compared to the amount of the proposed meal tray in order to take into account residents with a poor appetite for whom half portions are usually proposed.

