### 3.2 STUDY DIAGRAM

# 3.3 RANDOMIZATION

The randomization will be done via the Clinsight software by connecting to the website: https://nantes-lrsy.hugo-online.fr/CSOnline/.

The connection will be done thanks to a login, a password and a study number, delivered by a data-manager of the Research Promotion Department of the CHD of La Roche/Yon.

The following information must be filled in:

- First initial of the name
- First initial of the first name
- Date of birth
- Compliance with inclusion and non-inclusion criteria (yes/no)
- Collection of non-objection (yes/no).

The inclusion number will be assigned automatically during randomization. An e-mail confirmation will be sent to the person who performed the randomization and to all the persons concerned.

The randomization list will be carried out by a statistician from the Research Promotion Department of the CHD of La Roche/Yon.

A guide to the randomization procedure will be available online under Clinsight.

Randomization will be stratified by center (seniors's residents) and performed in a 1:1 ratio.

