# 4. STUDY POPULATION

# 4.1 DESCRIPTION OF THE POPULATION

All the residents of the CHD Vendée seniors's residents who meet the inclusion criteria will be able to be included in the "FIFO" trial:

- La Roche-sur-Yon : Le Marais, La Plaine
- Luçon : La Roseraie, L'Olivier
- Montaigu : Augereau, Le soleil de la Maine

Of the 269 residents institutionalized in these facilities, we estimate that about 60 subjects meet all the criteria.

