### Primary endpoint :

The evolution of caloric and protein intakes between inclusion and 6 months will be compared between the 2 groups by a Wilcoxon Mann-Whitney test.

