### 6.2.7 Choice of subjects to be included in analysis

All residents included in the study will be analyzed.

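### Section 6.2.5 names two single imputations for a missing primary intake without saying which one decides; if the group average fills most of the gaps, the 5% Wilcoxon test rejects too often.

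*Combined protocol and SAP*

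**What the plan says.** All references are to the combined protocol and SAP.

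- Section 2.1.3 measures caloric and protein intake before finger-food starts and then monthly to M6: "Quantitative measurement of ingesta (caloric and protein intake), monthly between M-1".
- Section 6.2.1, under the primary endpoint, gives the test: "The evolution of caloric and protein intakes between inclusion and 6 months will be compared between the 2 groups by a Wilcoxon Mann-Whitney test". Section 6.2.3 adds: "The significance level is set at 5" per cent.
- Section 6.2.5 describes the main criterion as "the comparison of the evolution of the quantity of ingesta between the inclusion and the 6 months of follow-up". Its whole missing-data rule is that "a missing value of these data will entail an imputation of this one by the worst value then, by the average of its group".
- Section 6.2.7 defines the analysis set: "All residents included in the study will be analyzed". Every missing M6 intake must therefore be filled.
- On size, section 4.1 says "we estimate that about 60 subjects meet all the criteria", and section 3.3 says randomization is "performed in a 1:1 ratio".

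Section 5.3.1 removes residents who no longer wish to take part. No section gives an expected withdrawal or missing rate, and section 6.2.6, on changes to the analysis strategy, is marked not applicable.

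**The concern.** The rule in 6.2.5 leaves three things open:

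1. **Order.** The two fills may be two successive analyses, or one analysis with a fallback. If they are two analyses, nothing says which p-value is the primary one.
2. **Meaning of 'worst'.** It could be the lowest value over both arms, the lowest in the resident's own arm, or the resident's own lowest value.
3. **What is filled.** It could be the M6 intake or the change. The M6 intake is the more natural reading, since the sentence speaks of a quantity of intake.

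These readings give different p-values, and the choice can still be made once the data are known. Under one of them the test does not hold its level. A value filled with the arm's own mean carries no new information, yet the test counts it as another resident, so a chance difference between the arms is counted more than once. The study is meant to supply preliminary data for later work (section 6.2.2), so a chance difference could look firmer than it is.

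**Working it through.** **Inputs.** From the plan: about 60 residents at 1:1, taken as 30 per arm; Wilcoxon Mann-Whitney test on the change; 5% level, taken as two-sided. Assumed, because the plan is silent: the missing rate (5 to 30%), missingness at random except where stated, normal intakes with SD 1, and correlation ρ of 0.5 or 0.7 between visits.

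**Step 1: the plan's own figure.** With complete data, the exact two-sided null distribution of U for 30 v 30 gives 4.96% at U ≤ 317 and 5.14% at U ≤ 318. The planned test therefore holds 5% when nothing is missing.

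**Step 2: why the group mean over-rejects.** Let n be the residents per arm, m those with an M6 intake, and f = m/n.

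*M6 intake filled.* The arm mean of the change is the mean of m M6 values minus the mean of n baselines.
- True variance: 1/m + 1/n − 2ρ/n = (1 + f − 2ρf)/(fn).
- Apparent variance, from the filled data: [f·2(1−ρ) + (1−f)]/n = (1 + f − 2ρf)/n.
- Ratio, true to apparent: 1/f, whatever ρ is.

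A mean-based test then rejects with probability 2[1 − Φ(1.96√f)]: 6.3, 8.0 and 10.1% for f = 0.9, 0.8 and 0.7.

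The spread is not reduced here. At f = 0.8 the within-arm variance of the change is 0.8×1.0 + 0.2×1 = 1.0 at ρ = 0.5, against 1.0 observed. At ρ = 0.7 it is 0.8×0.6 + 0.2×1 = 0.68 (SD 0.82), against 0.6 observed (SD 0.77). The excess comes from counting n residents where only m supplied an M6 value.

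*Change filled.* The true variance of the arm mean is σ²/m and the apparent one about fσ²/n, so the ratio is 1/f². Here the spread is understated as well. A mean-based test gives 2[1 − Φ(1.96f)]: 7.8, 11.7 and 17.0%. The Wilcoxon test does worse, because the filled values form one tied block per arm. At 20% missing, all 6×6 = 36 pairs between the two blocks fall the same way.

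**Step 3: simulation of the planned test.** No true effect, 20,000 trials per setting; ranges span ρ = 0.5 and 0.7; missing counts vary by chance unless stated. Complete data gave 4.5-5.2%.

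| Handling | 5% missing | 10% | 20% | 30% |
|---|---|---|---|---|
| Arm mean for M6 | 5.1-5.6% | 6.1-6.2% | 7.3-7.9% | 9.3-9.7% |
| Arm mean for the change | 6.4-7.3% | 9.2-9.5% | 17.3-17.8% | 31.4-31.5% |

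A separate simulation gave 5.9-6.1, 7.1-8.0 and 9.5-9.6% (M6) and 9.0-9.3, 16.6-17.8 and 30.3-30.6% (change) at 10, 20 and 30%. Observed cases gave 4.7-5.2%.

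Other readings:
- **One or two missing per arm, arm mean:** 5.0 or 5.3-5.4% (M6); 5.7 or 7.0% (change).
- **Resident's own worst, arm mean only as fallback:** 4.7-5.5%.
- **Share of missing M6 values given the arm mean** (20% missing, the rest own worst): 0, 25, 50, 75 and 100% give 4.6-5.1, 5.1-5.8, 5.9-6.4, 6.5-7.0 and 7.3-7.9%.
- **Common worst M6 value, equal rates:** 4.6-5.1%. With exactly equal counts it is conservative: 2.4-2.5, 1.1-1.3 and 0.5-0.8% at 10, 20 and 30%.
- **Common worst M6 value, 10% v 30% attrition:** 20-22% (15-16% with exactly 3 v 9 missing). The test then picks up the difference in attrition, not in intake.
- **Low eaters leaving more often in one arm** (10, 20, 30% missing in each arm): arm mean for M6 gives 6.3-6.8, 9.4-10.3 and 12.8-16.3%; observed cases give 4.7-5.1%.

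**Step 4: does the choice matter?** At 20% missing, the arm-mean and common-worst fills of M6 disagree on significance in about 8-9% of null trials, and in about 22% with 10% v 30% attrition.

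**The case against.** The harm is conditional. The group average must decide or fill most values, a material share of M6 intakes must be missing, and the largest figures also require that the change be filled. The plan names the worst value first, and the two fills may be meant as a sensitivity pair. The study is a pilot with no sample-size calculation, and no success rule hangs on the p-value. The English also looks translated, so the sentence may be clearer in the source language.

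Much of this stands. It limits the size of the problem and makes it a matter of correcting the text, not a proven failure. It does not remove it: 6.2.1 and 6.2.3 still set a formal 5% comparison, and no section says which fill decides. Naming the worst value first is no safeguard either, since a common worst value fails when attrition differs between arms.

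A reader might infer that mean filling always understates the spread. That holds only if the change is filled; with the M6 intake filled, the spread of the change is unchanged or larger (step 2).

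**Conclusion.** The concern holds in conditional form and should be fixed before analysis. Section 6.2.5 does not define the primary handling of missing intakes. If the group average fills most of them in the deciding analysis, a nominal 5% test rejects in about 6, 7-8 and 9-10% of null trials at 10, 20 and 30% missing (M6 filled), or about 9, 17-18 and 30-31% (change filled). These figures rest on 30 residents per arm, missingness at random and an assumed missing rate. The excess is zero if no M6 intake is missing.

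A reader might go further and conclude that this trial's type I error is 17% or 30%, or that the sponsor means to pick the favourable fill. The documents support neither: they give no missing rate, do not say that the group average decides, point more naturally to filling the M6 intake, and state no such intention. They only leave the choice open.

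**What to change.** 1. In 6.2.5, delete the group-average imputation.
2. Make the observed-case Wilcoxon test of the change from inclusion to M6 the single primary analysis, for calories and for protein. The test in 6.2.1 stays as it is.
3. In 6.2.7, state that residents without an M6 intake are described but are not in that test.
4. Add multiple imputation from arm, baseline and the monthly intakes as a sensitivity analysis, and add its mean-difference estimate to 6.2.1, because it does not use the Wilcoxon test.
5. Keep worst-value imputation only as a labelled sensitivity analysis, with one common value for both arms applied to the M6 intake.
6. Report deaths, withdrawals and missing M6 intakes by arm.

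**Cost.** Wording in 6.2.1, 6.2.5 and 6.2.7 and a little programming. No new data are needed, since intakes are already measured monthly. The ethics committee must be notified if the change is substantial.

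**Downside.** The observed-case test drops residents without an M6 intake and relies on missingness unrelated to outcome. It also loses the apparent power of mean filling. For an assumed 0.5 SD effect with 20% missing, rejections are 37-56%, against 45-61% (arm mean for M6) and 60-78% (arm mean for the change). Multiple imputation gives 40-59%, no clear gain over observed cases; its null rate was 3.8-4.9% at 10-30% missing at random.

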# 1. JUSTIFICATION OF THE STUDY

Undernutrition and the prevention of its risk in elderly people in seniors's resident constitute a major public health issue. The diagnosis of undernutrition and its risk are systematically recommended in these structures where the food of the persons is a problem because often unsuited to their capacities of grip and consequently to their nutritional needs. One of the solutions to remedy this could be the food offer proposed by the "finger-food".

The FIFO (Finger-Food) study, with a monocentric and randomized design, aims to verify the hypothesis that "finger-food" would increase food intake in seniors's residents with prehension disorders and/or requiring feeding stimulation and/or assistance with meal preparation.

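### Section 6.2.5 does not exempt a missing inclusion intake from the worst-value fill or define 'worst'; either reading inserts an extreme change and costs power

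*Combined protocol and SAP*

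**What the plan says.** Section 6.2.1 (primary endpoint) sets the analysis: "The evolution of caloric and protein intakes between inclusion and 6 months will be compared between the 2 groups by a Wilcoxon Mann-Whitney test". Section 6.2.5 describes the main criterion as "the comparison of the evolution of the quantity of ingesta between the inclusion and the 6 months of follow-up" and gives one rule for gaps: "a missing value of these data will entail an imputation of this one by the worst value then, by the average of its group". No visit is excluded. The section does not define 'worst', either as to scale (intake or change) or as to source (the resident, the arm or everyone).

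Three other places bear on the point:

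- Section 6.2.7: "All residents included in the study will be analyzed". A resident without an inclusion intake therefore stays in and needs a fill.
- Section 2.1.3: the baseline is a 3-day photographic record of lunch and dinner, taken "at a point in time between M-1 and M0". Section 5.1, Step 1, places this assessment before randomization.
- Section 3.3: the randomization form asks for initials, date of birth, compliance with the criteria and non-objection. It does not ask whether the baseline intake was recorded.

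**The concern.** A worst-value fill is normally chosen so that missing data cannot flatter a resident's result. That works for the month-6 intake, which enters the change with a plus sign. The inclusion intake enters with a minus sign. The study hopes to raise intake, so the natural meaning of the worst intake is the lowest one. Subtracting the lowest inclusion intake turns the cautious fill into a generous one for that resident.

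The other reading, in which the change itself is filled with the worst change, keeps the direction. It still discards a known month-6 value and puts the resident at the bottom of the ranking. Under either reading, residents with no baseline go to one end of the Wilcoxon ranking for a reason unrelated to treatment. With about 60 residents expected, a few such values can matter.

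**Working it through.** **Inputs from the documents.** About 60 eligible residents (Section 4.1), 1:1 allocation (Section 3.3), Wilcoxon Mann-Whitney test on the change (Section 6.2.1), 5% significance level (Section 6.2.3). Section 6.2.2 gives no sample-size calculation, so there is no planned power figure to reproduce.

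**Assumptions.** 30 per arm; two-sided test; normally distributed intakes with equal SD at both visits and correlation 0.6; baselines missing at random. For power, a true effect of 0.74 SD of change. Where kcal are given, mean 800 and SD 200. Only the worst-value fill is examined here, not the group-average fill.

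**Step 1: direction.** Change = month-6 intake − inclusion intake. Take a resident who goes from 900 to 950 kcal, in a group whose lowest intakes are 400 kcal at inclusion and 450 kcal at month 6, and whose worst change is −50 kcal.

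| Case | Change |
|---|---|
| Nothing missing | 950 − 900 = +50 |
| Month 6 missing, lowest month-6 intake used | 450 − 900 = −450 |
| Inclusion missing, lowest inclusion intake used | 950 − 400 = +550 |
| Inclusion missing, worst change used | −50 |

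The reversal in the third row follows from the minus sign alone. In simulation (4,000 runs), the lowest-intake fill at inclusion puts the filled change at about the 95th percentile of observed changes on average. At month 6 it puts it at about the 5th.

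**Step 2: power with 3 baselines missing in each arm.**

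| Fill for a missing inclusion intake | Power, about |
|---|---|
| Complete data | 77–78% |
| Mean of all observed inclusion intakes, arms pooled | 77% |
| Lowest intake | 67% |
| Worst change | 62% |

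The loss against the pooled mean is 77 − 67 = 10 points on the first reading and 77 − 62 = 15 on the second. With 1, 2 and 3 missing per arm, the lowest-intake fill gives 74.7%, 71.1% and 67.3%; the pooled mean gives 77.4%, 76.8% and 76.7%.

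**Step 3: no true effect, all gaps in one arm.** With 3 baselines missing in the finger-food arm only, the lowest-intake fill moves the mean difference by about +46 kcal. This is 3/30 of a gap of about 460 kcal (2.3 SD) between the average and the lowest inclusion intake: 0.10 × 460 = 46. Significant results favouring finger-food rise from about 2.3% to 7–8%. With the 3 gaps in control only, the shift is −45 kcal; 0.4% favour finger-food and 6.8% favour control. The worst-change fill reverses these signs: −41 kcal when the gaps are in finger-food, +41 kcal when they are in control. The pooled-mean fill stays at about 2.2–2.5% favouring finger-food.

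**Step 4: how likely is that split?** If 3 baselines are missing and allocation plays no part, the chance that all 3 fall in the finger-food arm is (30 × 29 × 28)/(60 × 59 × 58) = 24,360/205,320 = 11.9%. It is the same for control. When 3 gaps fall at random between arms, the rate of significant results favouring finger-food under the lowest-intake fill is 2.2–2.5%, against a nominal 2.5%. With 6 gaps it is 2.6–2.7%.

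**The case against.** A reader might infer that the rule turns a worst-case analysis into a best-case result for finger-food, and point to the 7–8% in Step 3. The documents do not support that. Section 5.1 puts the assessment before randomization, so gaps should not depend on arm. The one-sided split is a conditional case with a probability of about 12%, its mirror image is equally likely, and over random splits the error rate is nominal. Extreme gains go to individual residents, not systematically to an arm.

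The other side has four further arguments:

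- **The reversal depends on one reading.** Section 6.2.5 speaks of the evolution of intake, so the missing datum could be the change itself. That stands, and it is why the point is framed as an undefined term. It does not remove the cost, since the worst-change reading loses more power.
- **Missing baselines may be rare.** The 3-day record can be taken at any point in the M-1 to M0 window, and Section 12.3 has a monitor check primary-endpoint data at the end of inclusions. Both reduce the risk. Neither closes it: the form in Section 3.3 does not require the record, and monitoring cannot recover photographs that were never taken. No document suggests a rate; 3 per arm is an assumption.
- **This is a pilot with no planned power.** True: no stated figure is breached. The plan nevertheless tests its primary endpoint at 5%, and the loss is avoidable.
- **Section 6.2.5 also prescribes a group-average fill, which does not reverse.** True, but the worst-value fill is named first and remains part of the primary analysis.

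**Conclusion.** The point holds as a specification fault of moderate weight. The worst-value rule is undefined for the inclusion intake. On one reading it does the reverse of what it is for; on the other it imposes an extreme change despite a known month-6 value. The likely consequence is a loss of about 10 to 15 points of power under the assumptions above, plus distortion in either direction if gaps cluster in one arm by chance. It is not a bias toward finger-food or an inflated overall type I error. The reversal under the lowest-intake reading needs no numerical assumption; the percentages depend on the assumed correlation, effect size and number of gaps, and shrink as missing baselines become fewer. If none are missing, the issue disappears.

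**What to change.** In Section 6.2.5, limit the worst-value rule to a missing month-6 intake and define 'worst' there as the lowest observed month-6 intake. Add that a missing inclusion intake is filled with the mean of all observed inclusion intakes, both arms pooled. Pooling is appropriate because the value is assessed before randomization. Apply this to calories and protein alike.

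Optionally, add a yes/no item to the randomization form in Section 3.3 confirming that the M-1 intake was recorded, in line with the order set out in Section 5.1, Step 1.

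The cost is a sentence or two in Section 6.2.5 and, if adopted, one check box in Clinsight. The only downside is that a resident's randomization may wait a few days for the 3-day record. No visit, treatment or sample size changes.
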